7.2.2. Graded Laboratory Values

The Gilead Grading Scale for Severity of Adverse Events and Laboratory Abnormalities, Antiviral Toxicity Grade Scale, Version 01 April 2015 will be used to assign toxicity grades (0 to 5) to laboratory results for analysis. Grade 0 includes all values that do not meet the criteria for an abnormality of at least Grade 1. For laboratory tests with criteria for both increased and decreased levels, analyses for each direction (i.e., increased, decreased) will be presented separately.

For triglycerides, low-density lipoprotein, and cholesterol, toxicity grading scale is for fasting test values, so nonfasting lipid results (or lipid results without a known fasting status) will not be graded or summarized by toxicity grades.

7.2.2.1. Treatment-Emergent Laboratory Abnormalities

Treatment-emergent laboratory abnormalities (TELAs) are defined as values that increase at least 1 toxicity grade from baseline at any postbaseline time point during the TE period defined at the beginning of Section 7. If the relevant baseline laboratory value is missing, any abnormality of at least Grade 1 observed within the time frame specified above will be considered treatment emergent.

7.2.2.2. Summaries of Laboratory Abnormalities

Laboratory data that are categorical will be summarized using the number and percentage of participants in the study with the given response at baseline and each scheduled postbaseline visit.

The following summaries (number and percentage of participants) for TELAs will be provided by lab test; participants will be categorized according to the most severe postbaseline abnormality grade for a given lab test:

- Graded laboratory abnormalities
- Grade 3 or 4 laboratory abnormalities

For all summaries of laboratory abnormalities, the denominator is the number of participants with non-missing postbaseline values during the TE period defined at the beginning of Section 7.

A by-participant listing of TE Grade 3 or 4 laboratory abnormalities will be provided by participant ID number and visit in chronological order. This listing will include all test results

that were collected throughout the study for the lab test of interest, with all applicable severity grades and abnormal flags displayed.

7.3. Body Weight and Vital Signs

Descriptive statistics will be provided for body weight, BMI, and vital signs as follows:

- Baseline value
- Values at each postbaseline visit and time point
- Change from baseline at each postbaseline visit and time point

A baseline value will be defined as the last available value collected on or prior to the date/time of first dose of study drug. Change from baseline to a postbaseline visit and time point will be defined as the postbaseline value minus the baseline value.

In the case of multiple values in an analysis window, data will be selected for analysis as described in Section 3.8.3. At each visit, the body weight recorded repeatedly on multiple timepoints will be collapsed into one record. No formal statistical testing is planned.

A by-participant listing of vital signs will be provided by participant ID number and time point in chronological order. Body weight, height, and BMI will be included in the vital signs listing, if space permits. If not, they will be provided separately.

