7.7. Toxicity Management

7.7.1. Safety Monitoring Plan for CRS

As described in Section 1.4 and the VES IB, clinical signs and symptoms consistent with CRS have been reported in a minority of participants administered VES. Clinical manifestations include influenza-like symptoms such as fever, fatigue, chills, myalgias, and headache, which are generally transient and mild to moderate in severity. Infrequent but serious clinical manifestations that may be associated with CRS include hypoxia and hypotension and may require hospitalization and treatment. It is possible that administration of CAP256V2LS and VRC07-523LS in a sequential regimen with VES may increase the risk of CRS. The grading scale of CRS is shown in [Table 7](#).

Participants should be closely monitored for signs and symptoms of CRS during and after VES administration. For at least 24 hours following the first dose of VES and at least 4-8 hours following subsequent doses of VES, appropriately trained medical personnel and emergency equipment for the management of CRS should be on site and immediately available.

Following administration of VES, the participants will be monitored at the study site, and monitoring should include evaluation for signs and symptoms of CRS and assessment of vital signs (ie, blood pressure, pulse, respiration rate, oxygen saturation, and temperature) as follows:

First dose of VES (Day 0): Prior to administration of VES and then at 1, 2, 4, 8, 12, 18, and 24 hours after administration of VES, or if the participant experiences new or worsening symptoms, evaluate for signs and symptoms of CRS and vital signs.

Doses 2 of VES: Prior to administration and then at 1, 2, 4, and 8 hours after administration. If the participant experiences new or worsening symptoms, evaluate for signs and symptoms of CRS, including vital signs.

Dose 3 of VES: Prior to administration and then at 1, 2, and 4 hours after administration. If participants experience significant influenza-like AEs (eg, moderate or severe pyrexia, chills, headache, myalgia, fatigue, malaise, joint pain) after the first 2 VES doses, or if dose is escalated to 8 mg, monitoring may be extended to > 4 hours for subsequent doses. If the participant experiences new or worsening symptoms, evaluate for signs and symptoms of CRS, including vital signs.

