Doses of VRC07-523LS and CAP256V2LS: Prior to administration and at 1, 2, 4, and 8 hours after administration. If the participant experiences new or worsening symptoms, evaluate for signs and symptoms of CRS, including vital signs.

Doses 4 to 10 of VES: Prior to administration and at 1, 2, and 4, hours after administration. If the participant experiences abnormal vital signs, new or worsening symptoms, evaluate for signs and symptoms of CRS, including vital signs.

Following VES administration, treatment-related Grade 1 CRS with influenza-like symptoms such as fever, fatigue, chills, myalgia, or headache without more severe manifestations such as changes in blood pressure or oxygen saturation may be managed with supportive care at the clinical site (eg, acetaminophen [paracetamol] for myalgia or fever). Vesatolimod may be continued at the discretion of the investigator.

For \geq Grade 2 treatment-related CRS, including hypotension and/or hypoxia, immediate transfer to a hospital or emergency department for management in a monitored setting is advised. Administration of steroids, IV fluid for hypotension, and supplemental oxygen for hypoxia should also be considered. Vesatolimod may be continued at the discretion of the investigator and in consultation with the Gilead medical monitor.

Vesatolimod may be discontinued for treatment-related \geq Grade 3 CRS.

Table 7. The Common Terminology Criteria for Adverse Events (CTCAE) Version 5.0 Grading Scale for Infusion-related Reaction and Cytokine Release Syndrome

General Disorders and Administration Site Conditions					
CTCAE Term	Grade 1	Grade 2	Grade 3	Grade 4	Grade 5
Infusion-related reaction	Mild transient reaction; infusion interruption not indicated; intervention not indicated	Therapy or infusion interruption indicated but responds promptly to symptomatic treatment (eg, antihistamines, NSAIDS, narcotics, IV fluids); prophylactic medications indicated for \leq 24 hours	Prolonged (eg, not rapidly responsive to symptomatic medication and/or brief interruption of infusion); recurrence of symptoms following initial improvement; hospitalization indicated for clinical sequelae	Life-threatening consequences; urgent intervention indicated	Death

Definition: A disorder characterized by adverse reaction to the infusion of pharmacological or biological substances.

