3.8.2. Analysis Visits

The nominal visit as recorded on the eCRF or lab date will be used when data are summarized by visit. Any data relating to unscheduled visits will not be assigned to a particular visit or time point and in general will not be included in by-visit summaries. However, the following exceptions will be made:

- An unscheduled visit prior to the first dose of study drug may be included in the calculation of baseline value, if applicable.
- Unscheduled visits after the first dose of study drug will be included in determining the maximum postbaseline toxicity grade and time to event analyses.
- For participants who prematurely discontinued from the study drug, early termination (ET) data will be summarized as a separate visit, labeled as “Early Study Drug Discontinuation”.
- Data obtained after the follow-up visit or last exposure date (whichever is later) will be excluded from the summaries but will be included in the listings.

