3.8.3. Selection of Data in the Event of Multiple Records for a Visit

Depending on the statistical analysis method, single values may be required for each visit. For example, change from baseline by visit usually requires a single value, whereas a time-to-event analysis would not require 1 value per visit.

If multiple valid, non-missing, numeric measurements exist on the same nominal visit, records will be chosen based on the following rules if a single value is needed:

- In general, the baseline value will be the last non-missing value on or prior to the first dosing date of study drug, unless specified differently. If multiple measurements occur on the same day, the last non-missing value prior to the time of first dosing of study drug will be considered as the baseline value. If these multiple measurements occur at the same time or the time is not available, the average (geometric mean for HIV-1 RNA and arithmetic mean for others) of these measurements will be considered as the baseline value.

- For postbaseline visits, the value for the scheduled visit only will be used. If there is more than one record on the selected visit, the average will be taken (geometric mean for HIV-1 RNA and arithmetic mean for others), unless otherwise specified.

If multiple valid, non-missing, categorical measurements exist on the same nominal visit, records will be chosen based on the following rule if a single value is needed:

- For baseline, the last available record on or prior to the first dose of study drug will be selected. If there are multiple records with the same time or no time recorded on the same day, the value with the lowest severity will be selected (e.g., normal will be selected over abnormal for safety ECG findings).
- For postbaseline visits, the value for the scheduled visit only will be used. If multiple records are available for a scheduled visit, the most conservative value within that visit will be selected (e.g., abnormal will be selected over normal for safety ECGs).

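### SAP vital-sign tables can omit or dilute a symptom-triggered or rechecked post-dose reading, and give no worst post-dose value per participant, although these readings are taken to detect CRS

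*SAP*

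**What the plan says.** Protocol 7.7.1 states why the readings are taken: "Participants should be closely monitored for signs and symptoms of CRS during and after VES administration". Blood pressure, pulse, respiration rate, oxygen saturation and temperature are measured before each vesatolimod (VES) dose and at set hours afterwards. For the antibody infusions the times are "Prior to administration and at 1, 2, 4, and 8 hours after administration". Extra readings follow symptoms: "If the participant experiences new or worsening symptoms, evaluate for signs and symptoms of CRS, including vital signs".

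SAP 7.3 plans descriptive statistics of the baseline, of the value at every later visit and time point, and of change from baseline, plus a by-participant listing. Baseline is fixed once: "A baseline value will be defined as the last available value collected on or prior to the date/time of first dose of study drug". Multiple values are referred to SAP 3.8.3.

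SAP 3.8.2 says: "Any data relating to unscheduled visits will not be assigned to a particular visit or time point". Such data are in general kept out of by-visit summaries. The exception that covers data after the first dose reads "Unscheduled visits after the first dose of study drug will be included in determining the maximum postbaseline toxicity grade and time to event analyses".

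SAP 3.8.3, for numeric data after baseline and where a single value is required, uses the scheduled visit only and adds: "If there is more than one record on the selected visit, the average will be taken". For categorical data after baseline, the same section takes the most conservative record instead.

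**The concern.** CRS is a named risk of VES, and Protocol 7.7.1 accepts that this regimen may raise it. Protocol Table 7 grades CRS 1 to 3 on fever, hypotension and hypoxia, which these vital signs measure directly. Safety is the primary objective.

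The SAP handles these data less protectively than its other safety data. Laboratory abnormalities are categorised by the most severe grade (SAP 7.2.2.2), and ECG findings take the abnormal record over the normal one (SAP 3.8.3). Vital signs get no worst value, no threshold count and no grading. The SAP 3.8.2 exception for maximum toxicity grade therefore gives them nothing. The readings prompted by symptoms, or rechecked because they looked abnormal, are the ones most exposed to being left out or averaged.

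**Working it through.** The plan states no figure on this point, so there is none to reproduce. The check follows the rules through and illustrates their effect. Every temperature, saturation and pressure below is an assumption; the fever bands are those of Protocol Appendix 4 (Grade 1: 37.7 to 38.6 °C; Grade 2: 38.7 to 39.3 °C; Grade 3: 39.4 to 40.5 °C).

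**1. Which readings are scheduled**

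- Protocol 7.7.1: Dose 1 has 8 readings, the infusion day 5, Dose 2 5, Dose 3 4, and Doses 4 to 10 have 4 each. Total 8 + 5 + 5 + 4 + 7 × 4 = 50 per participant.
- Footnote l of the schedule (Protocol Appendix 2a, SAP Appendix 1): VES Doses 2 to 10 have 5 each, out to 8 hours. Total 8 + 5 + 9 × 5 = 58.
- The difference is the 8-hour reading at Doses 3 to 10: 58 − 50 = 8. The documents disagree on whether it is scheduled.

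**2. One febrile reading among 25 women, the other 24 at 36.8 °C**

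| Case | Her tabulated value | Mean | Maximum |
|---|---|---|---|
| Scheduled, not repeated: 39.4 °C | 39.4 | (24 × 36.8 + 39.4)/25 = 36.90 | 39.4 |
| Averaged with a 37.0 °C recheck at the same time point | (39.4 + 37.0)/2 = 38.2 | (24 × 36.8 + 38.2)/25 = 36.86 | 38.2 |
| 39.4 °C treated as unscheduled; her scheduled reading 36.8 °C | 36.8 | 36.80 | 36.8 |

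In the first case the maximum shows the event. In the second, a temperature in the Grade 3 band is tabulated as one in the Grade 1 band. In the third, the table shows nothing.

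**3. Range of the averaging effect**

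- Recheck 36.8 °C: (39.4 + 36.8)/2 = 38.1 °C, Grade 1 band.
- Recheck 39.0 °C: (39.4 + 39.0)/2 = 39.2 °C, Grade 2 band.
- Oxygen saturation: (88 + 98)/2 = 93%.
- Systolic pressure: (78 + 110)/2 = 94 mmHg.

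**4. The baseline**

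There are 11 dosing days: 10 for VES and 1 for the antibodies. On 10 of them, change is measured from an earlier day. Dose 10 is on Day 126, which is 126/7 = 18 weeks after the baseline reading and after treatment interruption has begun.

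Take 39.4 °C against a Day 0 value of 36.8 °C: the planned change is +2.6 °C. Against a same-day predose value of 36.3 to 37.3 °C, it would be +3.1 to +2.1 °C. The absolute 39.4 °C is tabulated either way.

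**The case against.** The strongest reply is that CRS is captured through adverse events. SAP 7.1.8 tabulates potential CRS and flu-like events by term and severity, from a list that includes pyrexia, hypotension, hypoxia and tachypnoea (SAP Appendix 4). Protocol 7.6 requires an abnormal vital sign accompanied by signs or symptoms to be recorded as an adverse event when it meets the definition, and a symptom-triggered reading is by nature accompanied by symptoms. The primary endpoints are adverse events and graded laboratory abnormalities. Vital signs are supportive, and Protocol 8.6 plans no analysis of them.

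That largely stands. It leaves open an abnormal reading without symptoms, or one judged not to be an adverse event. The planned adverse event tables are also not broken down by dose number, so they do not show the response to each dose.

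Three further limits stand.

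- Averaging applies only where a single value is needed. SAP 7.3 summarises by time point and expressly collapses only body weight, so averaging most plausibly affects repeats at one time point.
- SAP 3.8.2 speaks of unscheduled visits. Neither document says whether an extra reading during a scheduled dosing visit counts as unscheduled.
- Omission and averaging are alternatives. If the recheck is unscheduled, it is not averaged and the scheduled extreme stands.

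A reader might infer that fever, hypotension or hypoxia after a dose can vanish from the trial's tables, or that the Day 0 baseline conceals it. The documents do not support either reading. Absolute values with minimum and maximum are tabulated at each time point (SAP 3 and 7.3), including same-day predose. An event recorded as an adverse event is counted whatever the vital-sign rules do.

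**Conclusion.** The point holds in a limited form. An abnormal post-dose reading that is treated as unscheduled, or averaged with a recheck at the same time point, can be missing from or diluted in the vital-sign tables. If it was also not recorded as an adverse event, only the listing shows it. Separately, change from Day 0 is a poor measure of the response to later doses, though it hides no reading.

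How often this would occur cannot be derived from the documents. It depends on how symptom-triggered readings and rechecks are coded, and on how many are not reported as adverse events. The grade bands in the illustration show the size of the dilution only: the SAP does not grade vital signs, and adverse event severity is assigned by the investigator, not taken from an averaged value.

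This is a gap in a supportive safety summary and not an error in a primary endpoint. It is worth closing because safety is the primary objective and the data are already collected.

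**What to change.** In SAP 7.3, for each VES dose and for the antibody infusion day, add:

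- each participant's worst post-dose value (highest temperature, pulse and respiration rate; lowest systolic pressure and oxygen saturation) over all scheduled and unscheduled readings in that dose's post-dose monitoring period;
- change from the same-day predose value, as a supplement to change from Day 0;
- n (%) of participants by the existing fever grades of Protocol Appendix 4.

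Exempt these summaries from the averaging rule in SAP 3.8.3 and add them to the unscheduled-data exceptions in SAP 3.8.2. State how a symptom-triggered reading or recheck within a scheduled dosing visit is classified.

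Reconcile the post-dose vital-sign times for VES Doses 3 to 10, which run to 4 hours in Protocol 7.7.1 and to 8 hours in footnote l of the schedule, because they decide which readings count as scheduled.

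The cost is SAP wording and a few extra descriptive tables, with no new data collection. SAP 1 provides for changes after finalisation to be documented in the clinical study report.

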7.4. Prior and Concomitant Medications

Medications collected at screening and during the study will be coded using the current version of the World Health Organization (WHO) Drug dictionary.

7.4.1. Nonstudy Drug Antiretroviral Medications

Any nonstudy drug ARV medications used prior to, during, or after the study (if collected) are all recorded on the ARV eCRF. The WHO preferred name and drug code will be attached to the clinical database. All nonstudy drug ARV medications recorded on the ARV eCRF will be listed. No inferential statistics will be provided.

7.4.2. Concomitant Non-Antiretroviral Medications

Concomitant non-ARV medications (i.e., non-ARV medications other than study drug that are taken while receiving study drug) will be coded using the WHO Drug Dictionary. The WHO preferred name and drug code will be attached to the clinical database. Use of concomitant medications from the first dose date of study drug up to the last day of TE period will be summarized (number and percentage of participants) by WHO drug class and preferred name. Multiple drug use (by preferred name) will be counted only once per participant. The summary will be sorted alphabetically by drug class and then by decreasing total frequency within a class.

If the start or stop date of non-ARV medications is incomplete, the month and year (or year alone, if month is not recorded) of the start or stop date will be used to determine whether the non-ARVs are concomitant or not. The medication is concomitant if the month and year of the start or stop (or year of the start or stop, if month is not recorded) of the medication does not meet either of the following criteria:

- The month and year of start of the medication is after the last exposure date
- The month and year of stop of the medication is before the first dose date of study drug

If the start and stop date of non-ARV medications are complete, the start date is not after the last exposure date and the stop date is not before first dose date, or the non-ARV medications are marked as ongoing and start date is on or before the last exposure date, the non-ARV medications are concomitant.

Summaries of non-ARV concomitant medications will be based on the Safety Analysis Set. No formal statistical testing is planned. A by-participant listing for all non-ARV concomitant medications will be listed and sorted by participant ID number and administration date in chronological order.

7.5. Electrocardiogram Results

The investigator's assessment of ECG results (normal; abnormal; not clinically significant; abnormal, clinically significant) are collected at screening, end of period 3 visit for participants who have completed Period 3 or meet the ART restart criteria, and end of study visit for participants who have completed Period 4A or 4B. A by-participant listing for ECG assessment results will be provided by participant ID number.

7.6. Other Safety Measures

A by-participant listing of participant pregnancies during the study will be provided by participant ID number.

Although not necessarily related to safety, a by-participant listing of all comments received during the study on the comments form will be provided by participant ID number, and form for which the comment applies.

7.7. Changes From Protocol-Specified Safety Analyses

There are no deviations from the protocol-specified safety analyses.

8. PHARMACOKINETIC (PK) ANALYSES

8.1. PK Sample Collection and Concentration

PK concentration data from plasma PK samples of VES and serum PK samples of VRC07-523LS and CAP256V2LS collected at the timepoints stated in [Appendix 1](#) will be listed and summarized using the PK analysis set. PK concentration data from plasma PK samples of dolutegravir will be listed using the All Enrolled Analysis Set.

8.1.1. Estimation of PK Parameters

PK parameters will be estimated using Phoenix WinNonlin® software using standard noncompartmental methods. The linear up/log down rule will be used in conjunction with the appropriate noncompartmental model, with input values for dose level, dosing time, plasma concentration, and corresponding real-time values, based on drug dosing times whenever possible.

All predose sample times before time-zero will be converted to zero.

For area under the curve (AUC), samples BLQ of the bioanalytical assays occurring prior to the achievement of the first quantifiable concentration will be assigned a concentration value of zero to prevent overestimation of the initial AUC. Samples that are BLQ at all other time points will be treated as missing data in WinNonlin. The nominal time point for a key event or dosing interval (τ) may be used to permit direct calculation of AUC over specific time intervals. The appropriateness of this approach will be assessed by the PK scientist on a profile-by-profile basis.

Pharmacokinetic parameters such as AUC_{inf} , λ_z and $t_{1/2}$ are dependent on an accurate estimation of the terminal elimination phase of drug. The appropriateness of calculating these parameters will be evaluated upon inspection of PK data on a profile-by-profile basis by the PK scientist.

